7.5.4 Dose modifications for prolonged QTcF

All cardiac events should be treated as per the local standard of care and referred to a specialist if clinically indicated. Initial assessments will be made by the treating physician based on the QTc calculated by the ECG machine according to the Bazett formula ($QTcB = QT/\sqrt{RR}$). Any panobinostat dosing or withholding decisions will only be made after calculation of the QTcF according to the following formula $QTcF = QT/\sqrt[3]{RR}$ by trained research nurses or the principal investigator. If a patient cannot be dosed due to prolonged QTcF for more than 7 days since last dose, patient should be discontinued from study.

Table 7-5 Dose modifications for prolonged QTcF

ECGs to be performed at specified time point	Abnormality Noted	Dose Modification Guideline - At any time during a cycle of therapy (including intended day of dosing)
Dose modifications are based on local readings of the average QTcF* of triplicate ECGs. *QTcF: Heart rate corrected QT interval using the Fredericia formula: $QTcF = QT (msec) / \sqrt[3]{RR} (sec)$		
Pre-panobinostat-dose on cycle 1, day 1: 3 ECGs separated by 5-10 minutes, obtained prior to panobinostat dosing.	Average QTcF > 470 msec	
Check and correct the patient's serum potassium, magnesium, and calcium immediately, as well as evaluate con-meds that can prolong (or is known to be associated with) QTc interval.
 
Repeat 3 pre-panobinostat-dose ECGs. If the 3 pre-panobinostat-dose ECGs: Do not meet criteria again, discontinue patient from study. Do meet criteria for dosing; administer study drug treatment.

ECGs to be performed at specified time point	Abnormality Noted	Dose Modification Guideline - At any time during a cycle of therapy (including intended day of dosing)
Dose modifications are based on local readings of the average QTcF* of triplicate ECGs. *QTcF: Heart rate corrected QT interval using the Fredericia formula: $QTcF = QT (msec) / \sqrt[3]{RR}(sec)$		
Pre-panobinostat-dose on day 5, cycle 1, and on day 1 of subsequent cycles: 3 ECGs separated by 5-10 minutes, obtained prior to panobinostat dosing	Average QTcF: ≥ 481 msec to < 500 msec OR > 60 msec increase from baseline average	
Check and correct the patient's serum potassium, magnesium, and calcium immediately, as well as evaluate con-meds.
 
Delay panobinostat dose at least 3 days, hold MLN9708, and repeat 3 pre-panobinostat-dose ECGs.
 
If the repeat 3 pre-panobinostat-dose ECGs: Do not meet pre-panobinostat-dose ECG criteria again, discontinue patient from study. Do meet pre-panobinostat-dose ECG criteria for dosing and QT prolongation determined to be related to study drug, resume study drug treatment with a panobinostat dose reduction of 5 mg. If however, it was determined that the QT prolongation was secondary to electrolyte abnormalities or con-meds, continue at the same dose level upon correction of the electrolyte imbalance or discontinuation of the offending con-med. Repeat ECGs - pre-panobinostat-dose (x3), 3-hours post-panobinostat-dose (x3), on the next scheduled panobinostat dosing day.

Pre-panobinostat-dose on cycle 1, day 5 and on day 1 of subsequent cycles: 3 ECGs separated by 5-10 minutes, obtained prior to panobinostat dosing	Average QTcF ≥ 500 msec	
Check and correct the patient's serum potassium, magnesium, and calcium immediately.
 
Discontinue patient from study therapy.
 
If however, it was determined that the QT prolongation was secondary to electrolyte abnormalities or con-meds: Omit panobinostat and next MLN9708 dose. On the next scheduled panobinostat dosing day continue at the same dose level. Repeat ECGs - pre-panobinostat-dose (x3), 3-hours post-panobinostat-dose (x3), on the next scheduled dosing day.

ECGs to be performed at specified time point	Abnormality Noted	Dose Modification Guideline - At any time during a cycle of therapy (including intended day of dosing)

Dose modifications are based on local readings of the average QTcF* of triplicate ECGs. *QTcF: Heart rate corrected QT interval using the Fredericia formula:
 $QTcF = QT (msec) / \sqrt[3]{RR}(sec)$		

Post-panobinostat dose on cycle 1, days 1 and 5: 3 ECGs separated by 5-10 minutes, obtained 3 hours +/- 0.5 hours after panobinostat dosing:
	
Average QTcF \geq 481 msec to < 500 msec OR > 60 msec increase from baseline
	
Check and correct the patient's serum potassium, magnesium, and calcium immediately, as well as evaluate con-meds. Monitor ECG hourly or by telemetry until at least 2 consecutive hourly ECGs performed at least 6 hours post dose show QTcF < 481. Next scheduled panobinostat dosing day: repeat 3 pre-panobinostat-dose ECGs. If these 3 pre-panobinostat-dose ECGs: Do not meet pre-panobinostat-dose ECG criteria for dosing (average QTcF \leq 480 msec), discontinue patient from study. Do meet pre-panobinostat-dose ECG criteria for dosing (average QTcF \leq 480 msec) and QT prolongation determined to be related to study drug, resume study drug treatment with a panobinostat dose reduction of 5 mg. If however, it was determined that the QT prolongation was secondary to electrolyte abnormalities or con-meds, continue at the same dose level if responsible con-meds could be stopped and any electrolyte abnormalities are corrected. Repeat ECGs - pre-panobinostat-dose (x3), 3-hours post-panobinostat-dose (x3) on the next scheduled dosing day.

ECGs to be performed at specified time point	Abnormality Noted	Dose Modification Guideline - At any time during a cycle of therapy (including intended day of dosing)
Dose modifications are based on local readings of the average QTcF* of triplicate ECGs. *QTcF: Heart rate corrected QT interval using the Fredericia formula: $QTcF = QT (msec) / \sqrt[3]{RR}(sec)$		
	Average QTcF \geq 500 msec	
Check and correct the patient's serum potassium, magnesium, and calcium immediately.
 
Discontinue patient from study therapy and monitor ECG hourly or by telemetry until at least 2 consecutive hourly ECGs performed at least 6 hours post dose show QTcF < 480.
 
If however, it was determined that the QT prolongation was secondary to electrolyte abnormalities or con-meds: omit panobinostat and MLN9708 dose. On the next scheduled dosing day continue at the same dose level. Repeat ECGs - pre-panobinostat-dose (x3), 3-hours post-panobinostat-dose (x3), on the next scheduled dosing day.

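### Table 7-5: when QTcF of 500 msec or more is blamed on a con-med, the exception neither requires the drug to be stopped nor sets a limit for the repeat ECG

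*Combined protocol and SAP*

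**What the plan says.** Table 7-5 sets actions by time of reading and by average QTcF. Four of its cells contain a branch for prolongation traced to electrolytes or a con-med.

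- **Pre-dose, 481 to under 500 msec, or a rise above 60 msec.** Con-meds are evaluated, panobinostat is delayed, ixazomib is held and the triplicate is repeated. If the repeat fails: "Do not meet pre-panobinostat-dose ECG criteria again, discontinue patient from study". If it passes and the cause was electrolytes or a con-med: "continue at the same dose level upon correction of the electrolyte imbalance or discontinuation of the offending con-med".
- **Post-dose, same band.** Con-meds are evaluated. The repeat pre-dose triplicate must average 480 msec or less, otherwise the patient leaves the study. For the same causes: "continue at the same dose level if responsible con-meds could be stopped and any electrolyte abnormalities are corrected".
- **Pre-dose, 500 msec or more.** Electrolytes are corrected and the patient is discontinued, except that for these causes: "Omit panobinostat and next MLN9708 dose. On the next scheduled panobinostat dosing day continue at the same dose level".
- **Post-dose, 500 msec or more.** The default is the same, with hourly ECGs or telemetry on the day. The exception omits a dose of both drugs and then says "On the next scheduled dosing day continue at the same dose level".

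Both exceptions at 500 msec or more also order triplicate ECGs before dosing and 3 hours after dosing on the day of resumption.

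**The concern.** For a con-med cause, the exception gets looser as the reading gets worse. A patient at 485 msec goes back to the same dose only once the con-med is stopped and a repeat ECG passes. A patient at 510 msec with the same cause is directed back to the same dose with neither condition written. The text is not merely silent, because it affirmatively tells the site to continue. At stake is re-dosing a patient whose QTcF is still markedly prolonged while the responsible drug is still being taken, in a trial whose primary objective is tolerability and safety.

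**Working it through.** **1. The four branches side by side, for a con-med cause**

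| Stated in the cell | 481–499 pre-dose | 481–499 post-dose | ≥ 500 pre-dose exception | ≥ 500 post-dose exception |
|---|---|---|---|---|
| Evaluate con-meds | yes | yes | not stated (implied by the attribution) | not stated (implied) |
| Stop the responsible con-med | yes | yes | no | no |
| Correct electrolytes | yes | yes | yes | yes |
| Repeat pre-dose triplicate | yes | yes | yes | yes |
| Limit the repeat must meet | yes (pre-dose criteria) | yes (≤ 480 msec) | no | no |
| Off study if the repeat fails | yes | yes | no | no |

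In the 481–499 rows, failure of the repeat leads off study whatever the cause; cause is considered only once the repeat has passed. The cycle 1 day 1 pre-dose row (above 470 msec) has the same pattern. It tells staff to "evaluate con-meds that can prolong (or is known to be associated with) QTc interval", and if the repeat fails, "Do not meet criteria again, discontinue patient from study".

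**2. Rules elsewhere that might fill the gap**

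- Section 7.1.3 requires potassium, calcium and magnesium at or above the lower limit of normal before re-dosing. That closes the electrolyte side.
- Section 7.4 requires QTcF of 480 msec or less to start a new cycle, with an ECG mandatory before cycle 2. That covers cycle 2 day 1, not re-dosing within cycle 1.
- Exclusion 11 removes patients on any QT-risk drug that cannot be stopped or switched. It acts at entry.
- Sections 7.7 and 19 bar the drugs in Table 19-1. Section 19 leaves other QT-associated drugs to the investigator's discretion, with caution.
- Section 7.7.1 stops 5-HT3 blockers after QTcF prolongation. No other class has such a rule.
- Section 7.5.4 says "Any panobinostat dosing or withholding decisions will only be made after calculation of the QTcF", but that sentence gives no limit.
- Section 7.5.4 also removes a patient who cannot be dosed because of QTcF for more than 7 days since the last dose (timing below).

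**3. Timing**

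The scheduled readings left open are cycle 1 day 1 post-dose, day 5 pre-dose and day 5 post-dose. Panobinostat days are 1, 3, 5, 15, 17 and 19 (Table 5-1). Days from last dose to resumption:

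- Day 1 post-dose: the day 1 dose is already taken, so day 3 is omitted and day 5 is the resumption day. 5 − 1 = 4 days, so the 7-day rule cannot yet act. Day 5 has its own pre-dose row. A repeat of 481–499 msec meets the stricter rule there; a repeat of 500 msec or more blamed on the same con-med returns to the same exception.
- Day 5 pre-dose: day 5 is omitted, the last dose was day 3, and resumption is day 15. 15 − 3 = 12 days.
- Day 5 post-dose: day 15 is omitted and resumption is day 17. 17 − 5 = 12 days (15 − 5 = 10 if resumed on day 15).

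At 10 to 12 days the 7-day rule can act, but only if someone has judged that the repeat ECG bars dosing. The exception supplies no value for that judgment, and no pre-dose row names day 15 or 17.

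**4. Frequency**

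The documents give no rate for 500 msec or more. Section 1.2.5 (532 + 70 = 602 oral panobinostat patients) calls values above 480 msec infrequent and mostly seen at 60 mg every week. This trial gives 20 mg in alternate weeks.

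Section 2 reports one phase I value of 552 msec, labelled grade 1. The same paragraph gives a highest baseline of 430 msec and a largest rise of 13%, so the maximum should be 430 × 1.13 = 485.9 msec. A value of 552 would be a rise of at least 552/430 − 1 = 28.4%. The figure needs checking and is not relied on. Without it the count is 0/11 (exact 95% interval 0 to 28.5%); with it, 1/11 (0.2% to 41.3%).

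Assumed rate p among 20 phase II patients, with expected number 20p and chance of at least one 1 − (1 − p)^20:

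| p | Expected | At least one |
|---|---|---|
| 0.5% | 0.1 | 9.5% |
| 1% | 0.2 | 18.2% |
| 5% | 1.0 | 64.2% |

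These count any patient reaching 500 msec. Those with a qualifying con-med cause would be fewer; the documents do not say by how much.

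**The case against.** The best defence is that the rest of the plan makes the gap harmless. Discontinuation is the default at 500 msec. A mandatory pre-dose triplicate has little purpose unless it is judged against the 480 msec criterion that the neighbouring row states. The column heading applies the table at any time in a cycle, so a prolonged repeat can re-enter it. Patients may add no drug without consulting the investigator, cardiac events follow local standard of care, Section 7.5.1 allows clinical judgment, and a competent physician would stop the drug. Nothing here touches an endpoint.

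Most of that stands, and it makes the gap narrow. It does not close it. Judgment and standard of care allow a stop without requiring one, whereas the 481–499 rows do require it. Re-entry fails where it matters most, because a second reading of 500 msec or more blamed on the same con-med meets the same exception.

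A reader might infer more than the text supports:

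- That the plan is laxer overall at 500 msec. It is not; drug-related prolongation there ends treatment, and only the exception is looser.
- That the exceptions carry no safeguards. Electrolyte correction, an omitted dose and repeat triplicates are all written.
- That a patient could be re-dosed on day 3 after a day 1 reading. That would omit no panobinostat dose, so it does not fit the instruction.
- That exclusion 11 removes only listed drugs. It covers any QT-risk drug at entry, so the open group is mainly patients given a permitted drug afterwards.
- That the phase I dose-limiting toxicity result is in doubt. Nothing here bears on it.

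**Conclusion.** The point holds in a limited form. For a con-med cause, both exceptions at 500 msec or more lack three things that both 481–499 rows have: a requirement to stop the drug, a QTcF limit for the repeat ECG, and an action if it fails. The exposure is mainly a permitted QT-associated con-med, not a 5-HT3 blocker, in use around cycle 1 days 1 to 5. Few if any of the 20 phase II patients should meet it, though that rests on an assumed rate. This is a minor safety correction, worth making because it is cheap and the literal text could re-dose a patient at 500 msec or more with the offending drug still running.

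**What to change.** Add to both exceptions at 500 msec or more, pre-dose and post-dose:

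> Evaluate con-meds. Resume at the same dose only if the responsible con-med has been stopped, electrolytes are ≥ LLN, and the repeat pre-dose triplicate average QTcF is ≤ 480 msec and not > 60 msec above baseline; otherwise discontinue the patient from study.

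The 60 msec limb is included because it also triggers the lower rows; carrying over the 480 msec limit alone would leave the repeat ECG judged more loosely than a first reading.

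The cost is a short amendment to two cells. The repeat triplicates are already required, so no procedure is added. The downside is that an occasional patient who could have continued will leave the study, for example one whose con-med cannot be stopped.

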7.6 Management of Clinical Events

Infections

Mild infections may be treated with concurrent oral antibiotics of the beta-lactam class, with azithromycin or levofloxacin, or with other antibiotics taking possible pharmacokinetic interactions with panobinostat and MLN9708 into account. Infections that are associated with fever (temperature 38C on two consecutive measurements or one temperature of 38.5 C or higher) or with other concerning clinical signs or symptoms require holding all study drugs until the infection is controlled.

Nausea and/or Vomiting

Standard anti-emetics, including 5-HT₃ antagonists, are recommended for emesis occurring upon treatment initiation; prophylactic anti-emetics may also be considered. Dexamethasone should not be administered as an anti-emetic. Fluid deficits should be corrected before initiation of study drug and during treatment.

Diarrhea

Diarrhea should be managed according to standard clinical practice, including the administration of antidiarrheals once infectious causes are excluded. Fluid intake should be maintained to avoid dehydration. Fluid deficits should be corrected before initiation of treatment and during treatment.

Erythematous Rash With or Without Pruritus

As with VELCADE, rash with or without pruritus has been reported with MLN9708, primarily at the higher doses tested. The rash may range from some erythematous areas to macular and/or small papular bumps that may or may not be pruritic over a few areas of the body or more generalized, or it may have been transient and resolved either spontaneously or with standard symptomatic measures such as oral or topical antihistamines. Prophylactic measures should also be considered if a patient develops a rash (e.g., using a thick, alcohol-free emollient cream on dry areas of the body). In the case of rash, the use of a topical or oral steroid (e.g., prednisone ≤ 10 mg per day or equivalent) is permitted. A rare risk is Stevens-Johnson Syndrome, a severe, life-threatening or deadly rash with skin peeling and mouth sores, which should be managed symptomatically according to standard medical practice.

Thrombocytopenia

Thrombocytopenia has been reported with MLN9708 and panobinostat. Blood counts should be monitored regularly as outlined in the protocol with additional testing obtained according to standard clinical practice. Thrombocytopenia may be severe but has been manageable with platelet transfusions according to standard clinical practice. MLN9708 administration should be modified as noted as per dose modification recommendations in Table 3-2 and Table 7-4 when thrombocytopenia occurs. Therapy can be reinitiated at a reduced level upon recovery of platelet counts.

Neutropenia

Neutropenia has been reported with MLN9708 and panobinostat. Blood counts should be monitored regularly as outlined in the protocol with additional testing obtained according to standard clinical practice. GM-CSF and G-CSF may be used to shorten neutropenic periods and to maintain dose level of study drugs if neutropenia is the only reason for dose reduction according to table Table 7-4 and at the discretion of the treating physician.

Fluid Deficits

Dehydration should be avoided because MLN9708 and panobinostat may cause vomiting, diarrhea, and dehydration. Two cases of acute renal failure have been reported in patients treated at or above the MTD with IV administration of MLN9708. There has been no treatment-related renal failure reported in patients treated with PO MLN9708. Fluid deficits should be corrected before initiation of study drug and during treatment. Until further information is available, intake of NSAIDs while on this protocol should be avoided.

Hypotension

Symptomatic hypotension and orthostatic hypotension have been reported with MLN9708. Blood pressure should be closely monitored while the patient is on study treatment and fluid deficit should be corrected as needed, especially in the setting of concomitant symptoms such as nausea, vomiting, diarrhea, or anorexia. Patients taking medications and/or diuretics to manage their blood pressure (for either hypo- or hypertension) should be managed according to standard clinical practice, including considerations for dose adjustments of their concomitant medications during the course of the trial.

Posterior Reversible Encephalopathy Syndrome

One case of posterior reversible encephalopathy syndrome (PRES) has been reported with MLN9708. While this case ultimately resolved, PRES has also been reported rarely with another proteasome inhibitor, VELCADE. PRES is characterized by headache, seizures and visual loss, as well as abrupt increase in blood pressure. Prompt diagnosis and initiation of antihypertensive and anticonvulsant therapy are important to prevent irreversible end-organ damage.

7.6.1 Study drug discontinuation

It will be documented whether or not each patient completed the clinical study. If for any patient either study treatment or observations were discontinued, the reason will be recorded in the source documents and within ONCORE.

Patients will be informed that they have the right to withdraw from the study at any time for any reason, without prejudice to their medical care. The investigator also has the right to withdraw patients from the study for any of the following reasons:

1. Disease progression, this always requires removal from study
2. Adverse event(s)
3. Abnormal laboratory value(s)
4. Abnormal test procedure result(s)
5. For phase I patients only: Dosing delay of > 21 days (= unable to receive study therapy for 22 days including any therapy held during a cycle)
6. For phase I patients only: Delay of a cycle by > 14 days from the intended day of the next scheduled dose, counted from the start of the previous cycle.

7. Protocol violation
8. Subject withdrew consent
9. Lost to follow-up
10. Administrative problems
11. New anti-myeloma therapy started
12. Study Termination
13. Death

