3.2 Secondary Objective

- Assess response and clinical benefit response rates according to international uniform response criteria and adapted EBMT criteria, respectively (see under 8.1)
- Assess progression-free survival (PFS) and overall survival (OS)

4 Study endpoints:

4.1 Primary endpoints:

- Dose limiting toxicity (phase I) and tolerance according to CTCAE vs. 4.03 (phase I and II)

4.2 Secondary endpoints:

- Response to panobinostat, dexamethasone, ixazomib (MLN9708) will be assessed according to international uniform response criteria and clinical benefit response according to modified EBMT response criteria, comparing myeloma panels obtained at the beginning of each cycle that include SPEP, 24 h UPEP, serum and urine IFEs, and serum free light chains to results at screening. In addition a baseline bone marrow exam and skeletal survey will be obtained and repeated as clinically indicated and for assessment of complete remission (bone marrow).
- Progression-free survival will be measured from study entry to progression or death of any cause, whichever comes first.

- Overall survival for all will be measured from study entry to death from any cause.

5 Overall study design, treatment cycles, and study duration

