5.2 Study duration

Phase I: Patients will remain on study for six 28-day cycles or until criteria for discontinuation (7.6.1) are met, whichever comes earlier. Decisions on subsequent maintenance therapy will at the discretion of the treating physician. If the patient's myeloma is controlled in at least stable disease panobinostat may be continued free of charge to the patient. Follow up after completion of cycle 6 is at the discretion of the treating physician but if panobinostat is continued, monitoring for electrolyte abnormalities, especially potassium and magnesium, at a frequency appropriate for the respective patient, is recommended. This protocol may be amended to

include a formal maintenance phase and/or a phase II portion after review of safety and preliminary efficacy data.

Phase II: Patients will receive therapy according to DL2 and will remain on study until criteria for discontinuation (7.6.1) are met.

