7.6.2 Follow-up for toxicities

Patients whose treatment is interrupted or permanently discontinued due to a possibly study-drug related adverse event or abnormal laboratory value must be followed until resolution to CTCAE V 4.03 grade 2 or 30 days post last study drug administration, whichever comes first.

If a patient requires a dose delay of > 14 days from the intended day of the next scheduled dose, then the patient must be discontinued from the study. All patients will be followed for adverse events and serious adverse events for at least 4 weeks following the last dose of any study drug.

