2) Bone marrow examinations: In general this will only be done once at screening or within 28 days prior to study entry but for patients who appear to have reached a complete remission based on blood and urine studies it will be repeated for confirmation. Patients who have measurable disease only in the bone marrow will have bone marrow examinations after cycle 2 and at the end of the study. Additional bone marrow examinations may be obtained as clinically indicated. 3) Skeletal survey and left ventricular ejection fraction determination by Echocardiogram or MUGA scan: Within 28 days prior to study entry.

4) Vital sign assessment consists of height (first visit), pulse, blood pressure, respiration rate, temperature and weight. Blood pressure, pulse and respiration rate should be measured on patients after at least 3 minutes in the sitting position

5) ECGs:

- On Screening: One ECG
- On day 1 and 5 of cycle 1: Pre-dose: One ECG, Post-dose at 3 hours \pm 0.5 hour: One ECG
- On day 1 of cycle 2: Pre-dose: One ECG
- Additional ECGs as detailed under 7.5.4 may be necessary if QTcF prolongation prevents dosing of panobinostat and MLN9708 or if felt clinically necessary for other reasons

6) Pregnancy tests for females of childbearing potential. A female of childbearing potential (FCBP) is a sexually mature female who: 1) has not undergone a hysterectomy or bilateral oophorectomy; or 2) has not been naturally postmenopausal for at least 24 consecutive months (i.e., has had menses at any time in the preceding 24 consecutive months). All females of childbearing potential should complete a serum pregnancy test within 7 days prior to the administration of study drugs on day 1 of cycle 1. The pregnancy test should be repeated in week 1 of every cycle (except for cycle 1).

7) Compliance review / study calendar: Nurses review medication compliance based on study calendar patients fill out.

8) Study exit: Visits and assessments at study exit should occur within 3 days prior and 7 days after the end of the previous cycle or within 7 days after the decision to remove the patient from study. If grade \geq 3 non-hematologic adverse events or grade 4 neutropenia or thrombocytopenia are present at study exit, the respective adverse events should be followed weekly until resolution to grade 2 for non-hematologic adverse events and grade 3 for neutropenia and thrombocytopenia or until 30 days from last treatment have elapsed.

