10.4 Millennium Rules for Monitoring of Adverse Events and Period of Observation

AEs, both nonserious and serious, will be monitored throughout the study as follows:

- AEs will be reported from the first dose of MLN9708 through 30 days after administration of the last dose of MLN9708. In addition, skeletal-related events that occur during the follow-up periods must be reported from the first dose of MLN9708 through death or termination of the study by the sponsor-investigator or Millennium.
- Serious pretreatment events will be reported to Millennium Pharmacovigilance or designee from the time of the signing of the informed consent form (ICF) up to first dose of MLN9708.
- Related and unrelated SAEs will be reported to Millennium Pharmacovigilance or designee from the first dose of MLN9708 through 30 days after administration of the last dose of MLN9708. All SAEs should be monitored until they are resolved or are clearly determined to be due to a patient's stable or chronic condition or intercurrent illness(es). In addition, new primary malignancies that occur during the treatment or follow-up periods must be reported, regardless of causality to study regime. All new cases of primary malignancy must be reported to Millennium Pharmacovigilance (or designee). Follow up for detection of second primary malignancies beyond the planned study is not required; however, if the sponsor-investigator learns about the occurrence of a second primary malignancy in one of the study subjects within 3 years after the last study drug administration he must report the event to Millennium Pharmacovigilance (or designee).

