13.1.2.2 PFS and OS

Progression-free survival will be measured from study entry to progression or death of any cause, whichever comes first. Overall survival for all will be measured from study entry to death from any cause. Due to small sample size and limit of treatment duration to six months only observed PFS and OS will be reported for patients participating in phase I. For patients who enter on phase II the Kaplan-Meier method will be used to estimate PFS and OS.

14 Procedures and instructions

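### Phase II overall survival is to be a Kaplan-Meier estimate, but the plan sets no survival contact, cut-off or censoring rule after study exit

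*Combined protocol and SAP*

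**What the plan says.** OS is a secondary objective (Section 3.2). Section 4.2 defines it: "Overall survival for all will be measured from study entry to death from any cause". Section 13.1.2.2 repeats the definition and adds: "For patients who enter on phase II the Kaplan-Meier method will be used to estimate PFS and OS". Neither place gives a censoring rule or a data cut-off.

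Under Section 5.2, phase II patients "will remain on study until criteria for discontinuation (7.6.1) are met". The first reason listed in Section 7.6.1 is: "Disease progression, this always requires removal from study".

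The columns of Table 8-1 end at study exit. Footnote 8 places that visit around the end of the previous cycle or "within 7 days after the decision to remove the patient from study". The duties that run past exit are these:

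- Section 7.6.2: patients are "followed for adverse events and serious adverse events for at least 4 weeks following the last dose of any study drug".
- Section 10.1: more than 30 days after treatment stops, a serious adverse event goes to Novartis only if a causal link to treatment is suspected.
- Section 10.4: serious adverse events go to Millennium up to 30 days after the last ixazomib dose. Skeletal-related events in follow-up periods "must be reported from the first dose of MLN9708 through death or termination of the study by the sponsor-investigator or Millennium". New malignancies are also reportable, but "Follow up for detection of second primary malignancies beyond the planned study is not required".

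Section 12.2 ties the full manuscript to the last patient going off study. It still describes a study of up to 6 months, which does not fit phase II.

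**The concern.** A Kaplan-Meier OS curve needs, for every patient, either a date of death or a date last known alive. Most phase II patients can be expected to leave at progression, and most deaths to come after it. The plan schedules nothing that would record those deaths, or the survivors' dates, once the short safety window has closed.

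If patients are censored at exit, the censoring is informative, because progression is both the reason for leaving and a marker of higher risk of death. If later deaths are added when they come to light while survivors keep their exit date, the error can run the other way. The same 20 patients could give quite different medians, and the plan does not say which handling applies.

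**Working it through.** **No stated figure to reproduce.** The documents give no planned number of OS events, no OS follow-up time and no power for OS. The check has two parts: whether the elements exist, and how much their absence could matter.

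**Do they exist?**

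| Needed for OS | Nearest text | What it provides |
|---|---|---|
| Survival contact after exit | Sections 7.6.2 and 10.4 | At least 4 weeks for adverse events; skeletal events in undefined follow-up periods, with no contact interval and no vital-status record |
| Data cut-off | Section 12.2 | A publication trigger in phase I wording |
| Censoring rule | Sections 4.2 and 13.1.2.2 | None |

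Sections 10.3 and 14.2 were not in the text available. By their titles (adverse events of special interest; disclosure and confidentiality) they are unlikely to hold an OS plan.

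**How much could it matter? (illustration)**

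Inputs from the documents: event-free survival 5 months and OS 9 months (Section 2); 20 patients; about 18 months of accrual (Section 6). Assumptions: the 5 and 9 months are medians; times are exponential; accrual is uniform; a share *d* of first events are deaths, taken as 5-30% with no source in the documents. The Section 2 population is also more refractory than inclusion criterion 3 requires.

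The first-event hazard is *a* = ln 2 / 5 = 0.1386 per month. The post-progression death hazard *b* is set so that true OS is 50% at 9 months:

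S(t) = e^(−at) + (1 − d)·a·[e^(−at) − e^(−bt)] / (b − a), with S(9) = 0.5.

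*(a) Everyone censored a time τ after progression.* After the first τ months the hazard that Kaplan-Meier sees is constant:

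h = (d·a + b·q) / (1 + q), where q = (1 − d)·a·[1 − e^(−(b − a)τ)] / (b − a).

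Example, d = 0.10 and τ = 28 days = 0.92 month: b = 0.2384 and q = 0.1097, so h = (0.01386 + 0.02615) / 1.1097 = 0.0361. Then ln 2 / h = 19.2 months, or 19.5 once the lower hazard in the first month is allowed for.

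Deaths seen per 20 = 20·[d + (1 − d)(1 − e^(−bτ))].

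| d | Apparent median, τ = 28 days / 1 month | Apparent 12-month OS | True 12-month OS | Deaths seen per 20 |
|---|---|---|---|---|
| 0.05 | 21.8 / 20.7 | 69% / 67% | 35% | 4.9 / 5.2 |
| 0.10 | 19.5 / 18.7 | 65% / 64% | 35% | 5.5 / 5.8 |
| 0.20 | 15.9 / 15.5 | 59% / 59% | 36% | 6.8 / 7.0 |
| 0.30 | 13.3 / 13.1 | 54% / 53% | 37% | 8.1 / 8.3 |

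Simulation with 400,000 patients per setting gives 13.1-22.0 months. In simulated trials of 20 patients, the median exceeds 12 months or is not reached in 59-89% of trials, against 5-7% with full follow-up.

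Boundary: if the death hazard is the same before and after progression (0.077 per month, so d = 0.077 / 0.1386 = 5/9), the apparent median is 9.0 and there is no bias.

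*(b) Half of later deaths found, all others censored a month after progression* (simulation, cut-off 0-12 months after last enrolment): median 9.6-10.9 months.

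*(c) All later deaths found, survivors still censored a month after progression* (same simulation): median 8.4-8.9 months, below the truth.

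*With the fix.* Vital status to 12 months after last enrolment gives a median of 9.0 and about 17 of 20 deaths. Vital status to the last patient going off study gives about 18 of 20.

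**Sampling error for scale.** With 17 deaths, 9·exp(±1.96/√17) = 5.6 to 14.5 months.

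**The case against.** The strongest reply is that case (a) is not what the plan says. OS is defined for everyone through to death, and nothing tells the analyst to censor at progression. Section 7.6.1 is headed as drug discontinuation, it separates stopping treatment from stopping observation, and its list includes death and new therapy. It may therefore mean off treatment. The text uses the terms loosely elsewhere, as in Table 7-5, and Section 10.4 presupposes follow-up periods. The reporting rules to the two companies do not limit what the investigator may collect. Without case (a), the shifts are small beside sampling error. OS is secondary and uncontrolled in 20 patients, and no decision rests on it.

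Much of this stands. The wording is loose, the sizes are illustrative and depend heavily on *d*, and cases (b) and (c) are modest. A report showing only 5-8 deaths in 20 would also alert a careful reader to case (a).

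It does not remove the gap. Under either reading of off study, no text schedules a survival contact or says how survivors are censored. A low death count would reveal missing data without recovering it. Chart checks made at staff discretion are exactly the unplanned ascertainment at issue.

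**Conclusion.** The concern holds. The plan promises a Kaplan-Meier OS estimate for phase II and does not schedule the data it needs after exit. The missing text is certain; the size and direction of any error are not. Against a true 9 months, the apparent median could run from slightly low (8.4) to far too high (about 22), under the exponential model, the 5- and 9-month medians and the assumed 5-30% death share. Only censoring near progression produces an error that is large relative to sampling variation, and even that vanishes if progression does not change the death hazard. The primary safety objective and enrolment are unaffected. It should be fixed because OS is a stated endpoint, the repair is cheap, and dates last known alive may not be recoverable later.

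**What to change.** Leave the treatment-stopping rules as they are. Then:

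- In Section 7.6.1, separate leaving treatment from leaving survival follow-up.
- In Table 8-1, add one vital-status row for phase II patients after exit, by chart or phone, for example every 3 months until death or the cut-off.
- In Section 13.1.2.2, count deaths up to the cut-off and censor all other patients at the date last known alive by then.
- In Section 12.2, state the OS cut-off, for example 12 months after last enrolment or the last phase II patient going off study, and replace the 6-month wording.
- Define the follow-up periods named in Section 10.4 so that they agree with the above.

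The cost is an amendment, with the review Section 11 requires, and a little coordinator time for 20 patients. There are no procedures and no extra patients. Phase II was added in September 2015 with about 18 months of accrual expected, so some patients have probably exited by this April 2017 version. Phoning them may need ethics review or consent; chart review is simpler. With last patient off study as the cut-off, OS need not be later than the planned manuscript. A later cut-off would delay it.
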